### **5.8.6. Analysis of 12-Lead ECG**

Summaries of 12-lead ECG parameters by treatment group will include:

- Each ECG parameter and change from baseline
- The number (n) and percentage (%) of subjects with PCSV, depending on data
- ECG status (i.e. normal, abnormal) summarized by a shift table

Listings of ECG will be provided with flags indicating PCSVs.

## **5.9. Analysis of Pharmacokinetic Data**

The following analyses will be conducted:

- Descriptive statistics of functional dupilumab concentrations in serum at each sampling time by dose

- Graphical presentations of median and mean (+/- SD) functional dupilumab concentration in serum vs nominal time profiles
- Graphical presentations of individual functional dupilumab concentration in serum vs actual sampling time profiles
- Assessment of the impact of anti-drug antibodies on functional dupilumab concentrations in serum

No formal statistical analysis will be performed. For the descriptive statistical analysis, concentrations below the lower limit of quantitation (LLOQ) will be set to zero. When plotted on semi-log scale, concentrations are imputed as LLOQ/2. Mean data are presented by nominal time. Individual concentrations are presented by actual time.

## **5.10. Analysis of Immunogenicity Data**

### **5.10.1. Analysis of ADA Data**

Immunogenicity will be characterized by the ADA responses observed in patients in the ADA analysis set:

- Pre-existing immunoreactivity, defined as either an ADA positive response in the dupilumab ADA assay at baseline with all post first dose ADA results negative, OR a positive response at baseline with all post first dose ADA responses less than 4-fold over baseline titer levels
- Treatment-emergent response, defined as a positive response in the dupilumab ADA assay post first dose when baseline results are negative or missing
- Treatment-boosted response, defined as a positive response in the dupilumab ADA assay post first dose that is greater than or equal to 4-fold over baseline titer levels, when baseline results are positive
- Maximum Titer Values (Titer value category)
  - Low (titer <1,000)
  - Moderate (1,000 ≤ titer ≤ 10,000)
  - High (titer >10,000)

The following summaries will be provided:

- Number (%) of ADA-negative patients (pre-existing immunoreactivity or negative in the dupilumab ADA assay at all time points)
- Number (%) of treatment-emergent ADA-positive patients
- Number (%) of treatment-boosted ADA-positive patients

Listing of all ADA titer levels will be provided for treatment-emergent and treatment-boosted ADA response patients.

### **5.10.2. Analysis of Neutralizing Antibodies (NAb) Data**

The absolute occurrence (n) and percent of patients (%) with NAb positive or negative status will be provided by treatment group for patients in the NAb analysis set.

## **5.11. Analysis of Immunogenicity with Exposure, Safety and Efficacy**

### **5.11.1. Immunogenicity and Exposure**

Associations between ADA and systemic exposure to dupilumab will be explored. Plots of dupilumab concentration may be provided for analyzing the potential impact of treatment-emergent ADA responses and titer (high, moderate or low) on PK.

### **5.11.2. Immunogenicity and Safety and Efficacy**

Association between ADA and safety may be explored with a primary focus on the following safety events during the TEAE period:

- Injection site reaction (serious or severe and lasting 24 hours or longer)
- Hypersensitivity (SMQ: Hypersensitivity [Narrow])
- Anaphylaxis (SMQ: Anaphylaxis [Narrow])

Association between ADA and primary efficacy endpoints may be explored (e.g. scatter plot or spaghetti plot).

The above mentioned safety and efficacy analyses will be conducted using the following ADA response categories:

- ADA positive patients, that is patients with treatment-emergent or treatment-boosted response,
- ADA negative patients, that is patients with pre-existing immunoreactivity or negative in the ADA assay at all time points
- NAb positive patients, that is patients who were positive in the NAb assay at any time point analyzed.
- Maximum post-baseline titer level in treatment emergent or treatment boosted ADA positive patients:
  - High,
  - Moderate,
  - Low

## **5.12. Analysis of Biomarker Data**

All biomarker analyses will be performed on the FAS using all observed data. Descriptive statistics for the observed values, change from baseline and percent change from baseline values by treatment and visit will be provided for the biomarker variables.

The Wilcoxon signed-rank test will be used to test if the change or percentage change from baseline value is significantly different from zero. P-value will be reported.

Exploratory analyses for the difference between dupilumab groups and placebo on the change from baseline and percent change from baseline values will be performed using a rank-based ANCOVA model with treatment group and the relevant baseline values as covariate. Missing value will be imputed by LOCF method for visits between post-baseline to week 17. After week 17, no imputation will be made. P-value for difference between dupilumab +SCIT and SCIT will be provided.

Correlation of baseline serum Timothy Grass sIgE, Timothy Grass specific IgG, sIgG4, TARC and total IgE, absolute change or percent change at weeks 4, 8, and 17 from baseline in these biomarkers; with the following clinical endpoints will be explored using the Spearman's rho test. Both Spearman correlation coefficients and p-value will be reported. Correlation of baseline serum Timothy Grass sIgE, Timothy Grass specific IgG, sIgG4, TARC and total IgE with the following clinical endpoints will also be analyzed by the ANCOVA model with the clinical endpoint as the dependent variable and the baseline biomarker as the covariate, treatment group, and treatment group by baseline biomarker interaction as the factors. The missing values will be imputed using post-baseline LOCF. Similar correlation analysis will be performed for the subclasses of Timothy Grass sIgG other than sIgG4 pending on available data.

- Change and percent change from baseline in TNSS AUC post NAC over the first hour after the challenge (0-1 hr post peak TNSS) at week 17
- Change and percent change from baseline in TOSS AUC post NAC over the first hour after the challenge (0-1 hr post peak TNSS) at week 17
- Change and percent change from baseline (last pretreatment measurement) to week 17 in Skin Prick Test with Serial Allergen Titration, as measured by AUC of the average wheal sizes (diameter) after the challenge (early phase reaction)
- Change and percent change from baseline (last pretreatment measurement) to week 17 in the wheal size (diameter) induced by skin Timothy Grass intradermal injection 6 hrs after the challenge (late phase reaction)

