Dupilumab is a human monoclonal IgG4 antibody that inhibits interleukin-4 (IL-4) and interleukin-13 (IL-13) signaling by specifically binding to the IL-4R $\alpha$  subunit shared by the IL-4 and IL-13 receptor complexes. Blocking IL-4R $\alpha$  with dupilumab inhibits IL-4 and IL-13 cytokine-induced responses, including the release of proinflammatory cytokines, chemokines and IgE. IL-4 and IL-13 play key roles in the pathophysiology of allergic diseases, as demonstrated by dupilumab's efficacy shown in clinical studies in atopic diseases such as atopic dermatitis (AD), asthma, nasal polyposis (NP) and eosinophilic esophagitis. This is the basis for the rationale to evaluate whether dupilumab may enhance allergy immunotherapy. Dupilumab has clinically demonstrated down-modulation of the Type 2 pathway and has the potential to complement the immunoregulatory mechanisms of allergen immunotherapy. IL-4 and IL-13 are important cytokines that trigger class switching in B-cells (Lundgren M, 1989) and dupilumab has been shown to suppress serum total and specific immunoglobulin E (sIgE) over time in all studies where measured; serum total IgE decreased by ~30% after 12 weeks of weekly 300 mg treatment in AD; for sIgE, studies in AD and asthma patients show a ~40% reduction at week 16 and ~50% reduction at week 24 (Regeneron unpublished data). In a post-hoc analysis of a dupilumab dose-ranging study in moderate-to-severe asthma patients with comorbid allergic rhinitis, patients had a significant reduction in reported rhinitis symptoms with dupilumab compared to placebo. Because of these data and the role of IL-4 and IL-13 in immunoglobulin class switching, we anticipate that dupilumab as an adjunct to SCIT, will enhance the change of allergen specific IgG4/IgE ratio in SCIT + dupilumab treated subjects as compared to subjects treated with SCIT alone. In patients with AD, dupilumab modulated several Type 2 chemokines, including CCL17 (thymus and activation-regulated chemokine [TARC]) in serum and skin tissue, therefore we anticipate that dupilumab will modulate Type 2 chemokines and cytokines in subjects with a history of allergic rhinitis, which may improve tolerability of SCIT up-dosing (Beck, 2014) (Hamilton, 2014). A reduction in the production of Type 2 cytokines and chemokines by dupilumab is also likely to potentiate the reduction of provoked allergic rhinitis symptoms by SCIT.

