### 2.2. Sample Size and Power Considerations

[figure not shown]
Approximately 100 patients are planned to be randomized. It is estimated that with 25 subjects per group, the study will have 80% power to detect a difference of 29% between dupilumab plus SCIT and placebo plus SCIT with respect to percent change from baseline in TNSS AUC (0-1h) at week 17, assuming that the mean percent changes from baseline values are -55% and -26% for dupilumab plus SCIT and placebo plus SCIT, respectively, and a common standard deviation (SD) of 35%. The significance level is set to 2-sided, 0.05 level.

The assumptions used for primary endpoint were based on the study result from the Scadding (2017) study. The Scadding study shows after 1-year treatment, the difference between SCIT and placebo is 34% for the percent change in TNSS AUC (0-1h) at 1 year. A similar magnitude of improvement by adding dupilumab onto SCIT is assumed for the sample size calculation.

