### 4.5.2. Secondary Efficacy Variables

The secondary endpoints are:

- Change from baseline in TNSS AUC post NAC over the first hour after the challenge (0-1 hr post peak TNSS) at week 17 for dupilumab + SCIT as compared to SCIT
- Change and percent change from baseline in TNSS AUC post NAC over the first hour of the challenge (0-1 hr post peak TNSS) at week 17 for dupilumab as compared to placebo

- Change and percent change from baseline in the TNSS AUC post NAC over the first hour of the challenge (0-1 hr post peak TNSS) at week 17 for dupilumab + SCIT as compared to dupilumab
- Change and percent change from baseline (last pretreatment measurement) to week 17 in serum Timothy Grass sIgG4 for dupilumab + SCIT as compared to SCIT
- Change and percent change from baseline (last pretreatment measurement) to week 17 in serum Timothy Grass sIgE for dupilumab + SCIT as compared to SCIT
- Change from baseline (last pretreatment measurement) to week 17 in log-transformed value of serum Timothy Grass sIgG4 to Timothy Grass sIgE ratio for dupilumab + SCIT as compared to SCIT

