## **5.7. Analyses of Efficacy Variables**

For all efficacy variables, unless specified, the analysis will be comparisons of

- dupilumab + SCIT versus SCIT
- dupilumab versus placebo
- dupilumab + SCIT versus dupilumab for percent change and change in TNSS AUC only

The efficacy analyses will be based on the FAS Population. All statistical tests will be 2-sided at the 5% significance level. All confidence intervals (CIs) will be 2-sided 95% CIs.

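### The within-arm signed-rank test on percent change in biomarkers leans towards increases and against falls; it should be run on ln(visit/baseline) (minor)

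*SAP*

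**What the plan says.** SAP 5.12 (Analysis of Biomarker Data) summarises observed values, change and percent change by arm and visit. It then adds a within-arm test: "The Wilcoxon signed-rank test will be used to test if the change or percentage change from baseline value is significantly different from zero". A p-value is to be reported. The section does not say which of the two scales decides, and it plans no log-ratio version for sIgE, sIgG4, sIgG, total IgE or TARC.

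The log scale is used only for the two antibody ratios. For one of them, SAP 4.5.2 specifies the change "in log-transformed value of serum Timothy Grass sIgG4 to Timothy Grass sIgE ratio".

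Section 5.12 sets no significance level of its own. SAP 5.7 states, for the efficacy variables, "All statistical tests will be 2-sided at the 5% significance level". SAP 5.7.3 applies no multiplicity control.

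The between-arm biomarker comparison is a separate rank-based ANCOVA (SAP 5.7.2 and 5.12).

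On expected effects, Protocol 1 reports for sIgE that "studies in AD and asthma patients show a ~40% reduction at week 16 and ~50% reduction at week 24", and for total IgE that "serum total IgE decreased by ~30% after 12 weeks of weekly 300 mg treatment in AD". Protocol 3.2.8.5 gives a larger figure for total IgE, about 50% at 12 to 16 weeks. Protocol 3.2.8.1 describes a two-fold rise in sIgG4 after SCIT starts. No variability is stated for any biomarker.

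**The concern.** Under its null, the signed-rank test needs a distribution that is symmetric about zero. If nothing has changed, so that baseline and follow-up are exchangeable, ln(visit/baseline) is symmetric and so is the absolute difference. Percent change is not. A doubling and a halving are equal and opposite on the log scale, but they score +100% and −50%, so the doubling takes the higher rank. Across a sample this pushes the statistic upwards.

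At stake are the within-arm p-values for markers that carry the mechanistic account. Under no change, spurious increases are declared more often than the 2.5% intended. Falls in sIgE, total IgE and TARC, which the protocol predicts with dupilumab, become harder to show.

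**Working it through.** **The plan's own figure.** The only power statement is for the primary endpoint: "It is estimated that with 25 subjects per group, the study will have 80% power to detect a difference of 29" percentage points, "and a common standard deviation (SD) of 35". The noncentrality is (29/35) × √(25/2) = 2.93. With 48 degrees of freedom and two-sided 0.05, a two-sample t-test has power 81.9%, in line with the stated 80%. This confirms n = 25 per arm as the working size. It does not bear on the biomarker test, for which no power is stated.

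**Direction, without a distributional model.** Let x = ln(visit/baseline), so percent change = 100(eˣ − 1). The positive rank sum W⁺ equals the number of pairs i ≤ j with a positive pairwise sum. If xᵢ + xⱼ > 0, then e^xᵢ + e^xⱼ ≥ 2e^((xᵢ+xⱼ)/2) > 2, so the percent-change sum for that pair is positive too. Hence, in any data set, W⁺ on percent change is at least W⁺ on the log ratio.

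**Inputs for the size.**
- n = 25 per arm (SAP 2.2).
- Two-sided 5%, borrowed from SAP 5.7. The exact critical value is W ≤ 89, with attained level 4.83%.
- SD of x: **not in the documents**. It is assumed and shown over a range, with x normal.
- Falls of 30%, 40% and 50%, from the protocol figures above, entered as mean x = ln(0.7), ln(0.6) and ln(0.5).

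The results below come from simulating the exact test with 30,000 to 60,000 runs per cell. Repeat runs move them by a few tenths of a point in the first table, and by up to about one point in the second.

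**No true change, test on percent change:**

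| Assumed SD of x | False increase (2.5% intended) | False decrease (2.5% intended) | Two-sided |
|---|---|---|---|
| 0.1 | 3.1% | 1.9% | 5.0% |
| 0.2 | 3.8% | 1.5% | 5.3% |
| 0.3 | 4.7% | 1.3% | 6.0% |
| 0.5 | 6.7% | 0.9% | 7.6% |
| 0.7 | 9.2% | 0.6% | about 9.8% |
| 1.0 | 12.9% | 0.4% | 13.3% |

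On the log ratio, each tail is about 2.4% at every SD. With a heavier-tailed null (t with 5 degrees of freedom), the tilt remains: 5.5% / 1.1% at SD 0.5 and 7.2% / 0.7% at SD 0.7.

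**Power to show a true fall, log ratio against percent change:**

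| Assumed SD of x | 30% fall | 40% fall | 50% fall |
|---|---|---|---|
| 0.4 | 98.7 vs 94.8% | 100 vs 99.9% | 100 vs 100% |
| 0.5 | 91.9 vs 77.6% | 99.7 vs 97.8% | 100 vs 100% |
| 0.6 | 79.1 vs 55.2% | 97.8 vs 88.7% | 100 vs 99.2% |
| 0.7 | 66.4 vs 37.9% | 92.6 vs 72.8% | 99.6 vs 95.2% |
| 1.0 | 38.1 vs 12.5% | 66.5 vs 30.4% | 89.8 vs 58.6% |

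A loss of 10 points or more starts at an SD of about 0.5 for a 30% fall, just above 0.6 for 40%, and about 0.8 for 50%.

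**Absolute change as the alternative.** Under exchangeability it holds its level (2.3% to 2.5% per tail, assuming an SD of log baseline of 1). If instead the fold change is independent of baseline, it is tilted as well. At SD 0.7 and the same baseline SD, false increase / decrease is about 6.0% / 0.9%, and power for a 40% fall is 72% to 73%, no better than percent change.

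**Between-arm test.** 100(eˣ − 1) rises strictly with x, so ranking percent change gives the same response ranks as ranking the log ratio.

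**The case against.** The strongest reply has four parts.

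1. *The same sentence also allows absolute change, which is valid under exchangeability.* This stands, so it would be wrong to infer that the plan tests these markers on the percent scale only. It does not settle the matter. The SAP does not say which version governs, and absolute change loses its level when the fold change does not depend on baseline.

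2. *The expected falls would be found anyway.* A reader might infer that the test forfeits much of the power to show the falls the protocol predicts. The documents do not support that as a general statement. For falls of 40% to 50%, the loss is 2 points or less up to SD 0.5. The 30% figure, where losses start earlier, comes from weekly dosing in atopic dermatitis, and Protocol 3.2.8.5 puts the fall in total IgE nearer 50%.

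3. *No source shows that log-scale SDs reach 0.7 to 1.0.* True. At SD 0.2 or below the two-sided level is about 5.0% to 5.3%, with only the tails unbalanced. The larger figures are conditional.

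4. *Nothing important rests on these p-values.* Largely true. The biomarker secondary endpoints are between-arm comparisons by rank ANCOVA. In the SCIT arms a two-fold sIgG4 rise is expected, and either scale would show a true doubling with over 99% power up to SD 0.7. False increases matter mainly where no rise is expected, such as sIgG4 in the arms without SCIT.

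These points limit the size and reach of the problem. None makes the percent-change version a valid test of no change.

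**Conclusion.** The point holds as a minor one. Against a null of exchangeable baseline and follow-up, the percent-change signed-rank test is tilted towards increases and against falls, and that direction needs no lognormal assumption.

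The amount is conditional on the unstated SD of ln(visit/baseline), on n = 25 with complete data, and on a 5% two-sided level carried over from SAP 5.7. The imbalance is modest at SD 0.2. At SD 0.3 the false-increase rate is already nearly twice the intended 2.5%, although the two-sided level still looks close to nominal. The two-sided level is clearly inflated from SD 0.5 upward. The power loss is material for a 30% fall from about SD 0.5, and for larger falls only at higher variability.

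The consequence is confined to supplementary within-arm p-values. A reader might go on to doubt the between-arm biomarker results or the TNSS conclusion. Neither doubt follows: the rank ANCOVA sees the same response ranks on either scale, and the primary analysis does not use this test.

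**What to change.** In SAP 5.12, specify that the within-arm signed-rank test is applied to ln(visit/baseline) for sIgE, sIgG4, sIgG, total IgE and TARC, and that this version governs. Keep percent change as a descriptive summary without a p-value. Do not fall back on absolute change alone, since it is also tilted when the fold change is independent of baseline.

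The logarithm needs positive values, and Protocol 3.2.8.1 notes that sIgG4 may be undetectable before SCIT. The same edit should therefore name the substitute for results below the quantitation limit. The SAP has such a rule only for dupilumab concentrations (5.9), and percent change would need one for undetectable baselines too.

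The cost is a sentence or two in the SAP and about one line of code. No new data are needed, and the log scale is already in use for the two antibody ratios. With the change, each tail returns to about 2.4%.

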### 3.2.8. Rationale for Other Endpoints

#### 3.2.8.1. Ratio of Allergen-Specific IgG4 to IgE in Serum

Immunotherapy induces both cellular and humoral regulatory immune mechanisms. Humoral mechanisms involve the induction of allergen specific antibodies, especially of the IgG4 isotype, which is thought to have a protective effect against IgE-mediated allergic symptoms. IgG4 competes with IgE, blocking IgE-mediated effector cell activation, suppresses histamine release and inhibits antigen-presentation of IgE-allergen complex by dendritic and B-cells (James, 2012). The gradual increase in serum allergen-specific IgG4, IgE-blocking factor and decrease in allergen-specific IgEs have been associated with clinical desensitization in SCIT for grass (Shamji, 2012) and was consistently observed across different studies. At the start of SCIT, serum sIgG4s are low/undetectable. In response to the initiation of SCIT, a 2-fold increase in sIgG4 and a transient increase in sIgE is observed (Scadding, 2017) (Creticos, 1992)

(Suarez-Fueyo, 2014). An approximately 8-fold increase in the ratio of sIgG4/sIgE was associated with a reduction in symptoms induced by nasal allergen provocation after 1-year of SCIT (Scadding, 2017). A higher ratio of sIgG4/sIgE in patients tolerant to some allergens (eg, birch, cat, peanut) compared to their symptomatic controls was observed (Geroldinger-Simic, 2011) (Du Toit, 2013) (Burnett, 2013). Compared to the individual levels of sIgG4 or sIgE, the ratio of sIgG4/IgE is thought to be more reflective of the competition for allergen binding between IgG4 and IgE and has so far shown better correlation with clinical improvement. Given that the induction of sIgG4 and the suppression of sIgE is the most well-known phenomenon associated with immunotherapy and dupilumab has been shown to suppress specific IgE in past studies, we aim to test if skewing of sIgG4/IgE ratio will be one of the immunological effects of dupilumab as an adjunct to SCIT treatment.

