### **3.2.8.4. Serum TARC and Total IgE**

Serum TARC and total IgE are markers of Type 2 immune activity. Dupilumab significantly suppressed both TARC and total IgE in studies of adult AD, NP, and asthma patients.

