#### **3.1. The Full Analysis Set (FAS)**

The full analysis set (FAS) includes all randomized patients. Efficacy analyses will be based on the treatment allocated at randomization (as randomized).

FAS is the primary analysis set for efficacy endpoints.

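### The planned Spearman correlations of biomarker change with clinical change have no term for treatment arm, so treatment effects alone can produce a significant correlation

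*SAP*

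**What the plan says.** SAP Section 5.12 sets the population: "All biomarker analyses will be performed on the FAS using all observed data". SAP Section 3.1 defines it: "The full analysis set (FAS) includes all randomized patients". All four arms are therefore included.

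The markers are sIgE, sIgG, sIgG4, TARC and total IgE. They enter at their baseline level and also as "absolute change or percent change at weeks 4, 8, and 17 from baseline in these biomarkers". For both forms the plan is the same: correlation "with the following clinical endpoints will be explored using the Spearman's rho test". Coefficients and p-values are to be reported. The clinical endpoints are the week-17 changes in TNSS AUC, TOSS AUC, skin prick response and intradermal response. No treatment term, stratum or by-arm calculation is mentioned.

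The next sentence of Section 5.12 adds an ANCOVA with "the baseline biomarker as the covariate, treatment group, and treatment group by baseline biomarker interaction as the factors". It covers baseline biomarkers only and does not extend to biomarker changes.

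The protocol expects treatment to move these markers. Section 3.2.8.4 says "Dupilumab significantly suppressed both TARC and total IgE in studies of adult AD, NP, and asthma patients". Section 1 cites a fall in sIgE of about 40% at week 16. Section 3.2.8.1 says that after SCIT is started "a 2-fold increase in sIgG4 and a transient increase in sIgE is observed".

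**The concern.** Baseline biomarkers are balanced across arms by randomization. Changes after randomization are not, because treatment is meant to alter them. The plan therefore includes treatment group where it matters less and omits it where it matters more.

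If one treatment lowers a marker and also lowers TNSS, its recipients sit low on both axes and the others sit high on both. A rank correlation over everyone is then non-zero even when, within each arm, subjects with larger marker changes do no better than the rest. The reported p-value would be read as evidence that the marker tracks symptom relief, when it may only restate that the arms differ on both measures. What is at stake is the mechanistic reading of the biomarker results.

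**Working it through.** **The plan's own figure.** SAP Section 2.2 gives 25 per arm, means of −55% and −26%, SD 35%, two-sided 0.05 and 80% power. The noncentrality is 29 / (35 × √(2/25)) = 29 / 9.90 = 2.93. On 48 df the t-test power is 81.9% (83.4% by the normal approximation), so the t-test reproduces the stated 80% to within 2 points. The SAP gives no figure for the correlations.

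**Inputs.**
- From the documents: four arms of 25; dupilumab effect on top of SCIT of 29 points; SD 35; SCIT arm mean −26.
- Assumed: no change in the placebo arm, so that SCIT's effect is 26 points; additive effects, so that dupilumab alone is at −29; normal data; marker shifts of 0.25 to 2 within-arm SD; within-arm correlation exactly zero.

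**Approximate size of the pooled correlation.** Let the TNSS effects in SD units be a = 29/35 = 0.829 (dupilumab) and b = 26/35 = 0.743 (SCIT). Suppose dupilumab shifts the marker by s SD. Half the subjects receive each treatment, so

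r ≈ (s·a/4) / √[(1 + s²/4)(1 + a²/4 + b²/4)].

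For s = 1: 0.207 / √(1.25 × 1.310) = 0.207 / 1.280 = 0.16. For a SCIT-driven marker the numerator is s·b/4 = 0.186, which gives 0.15 in size. The sign is negative when SCIT raises the marker.

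**Rejection rates at nominal 5%.** 20,000 simulated trials per scenario; pooled Spearman against a partial Spearman adjusted for arm (ranks centred within arm, 95 df):

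| Marker shift | Pooled, dupilumab-driven | Pooled, SCIT-driven | Adjusted for arm |
|---|---|---|---|
| 0.25 SD | 7% | 7% | 5% |
| 0.5 SD | 14% | 12% | 5% |
| 1 SD | 37% | 31% | 5% |
| 2 SD | 77% | 67% | 5% |

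With half the TNSS effects, the rates for shifts of 1 to 2 SD fall to about 12–30%. With no TNSS effect, both methods reject about 5%.

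**Check from the documents' own marker effects** (3,000 trials per scenario, same TNSS means; marker SDs assumed):
- sIgE falls 40 points with dupilumab; SD 20/40/60 points: pooled test significant in 78%/36%/19%.
- sIgG4 doubles with SCIT; log SD 0.35/0.7/1.0: 66%/29%/18%.
- Placebo mean instead at −26 + 34 = +8, from the 34-point SCIT-versus-placebo difference cited in SAP Section 2.2, with dupilumab alone at 8 − 29 = −21: sIgE 74%/34%/18%, sIgG4 88%/45%/25%.
- Only the two SCIT arms combined (50 subjects), sIgE SD 20/30/40/60: 51%/33%/22%/15%.
- Dupilumab without any effect on TNSS: the sIgE correlation stays at 4–5%.

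Adjusted for arm, every scenario gives a mean correlation of about zero and a rejection rate of 4–6%.

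**Opposing effects.** If dupilumab lowers sIgE by 1 SD and SCIT raises it by 0.5 SD or 1 SD (assumed), the pooled rate falls from about 37% to 14% or 5%.

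**The case against.** The SAP never says the arms are pooled. The opening of SAP Section 5 says data are summarized by the four treatment groups. In Section 5.12 the signed-rank test of change from zero also names no arm, although it makes little sense except by arm. Run by arm, the correlations would not have this artefact. This stands in part: pooling is an inference. However, the general line concerns summaries, and Section 5.12 does specify treatment and visit for its descriptive statistics but not for the correlations. If by-arm was meant, the text needs to say so. With 25 subjects the power for a true rho of 0.4 is about Φ(0.424 × √22 − 1.96) = 51%. An arm-adjusted analysis of 100 has about 98%, provided that rho is common to all arms.

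The size is also open to challenge, and that challenge stands. The 26/35 SD used for SCIT is not a planning value for SCIT versus placebo: −26% is a change from baseline within the SCIT arm. No document supports marker shifts of 1 to 2 SD in particular. Smaller shifts are plausible at weeks 4 and 8, since SCIT reaches its planned maintenance dose only at week 8. For sIgE the protocol describes SCIT and dupilumab acting in opposite directions.

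A reader might also infer that most of any observed correlation would be between-arm. The simulations cannot show this, because they set the within-arm association to zero by construction. Finally, SAP Section 4.9 gives the aim as understanding pathophysiology and mechanism of action, and between-arm co-movement is a legitimate part of that description. A pooled coefficient may therefore be shown, if it is labelled for what it is.

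**Conclusion.** The point holds on the natural reading of Section 5.12. A Spearman test of biomarker change against clinical change over all arms, without a term for arm, does not hold its nominal level when a treatment moves both variables. The existence of the artefact requires only that. Its size cannot be fixed from the documents: under the stated assumptions the rejection rate runs from about 7% to 77% across shifts of 0.25 to 2 SD. It is lower with smaller TNSS effects or opposing marker effects, and about 5% after adjustment for arm.

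The documents do not support the stronger reading that the SAP prescribes pooling, or that the upper rates are the expected ones. Nor is there any threat to the trial's main results: these correlations are exploratory and feed no primary or secondary conclusion.

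**What to change.** In SAP Section 5.12, for biomarker changes at weeks 4, 8 and 17:
- Make the inferential analysis arm-adjusted. Either use a partial Spearman correlation (rank both variables, regress each set of ranks on the four-level treatment group, correlate the residuals), or extend the ANCOVA already specified for baseline biomarkers, with its "treatment group by baseline biomarker interaction as the factors", to biomarker change.
- Show within-arm coefficients descriptively.
- Label any coefficient pooled over arms as including between-arm differences.

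The cost is about one SAP sentence and a small programming change; no new data are needed. The drawback is that a single partial rho assumes a similar association in every arm. The within-arm coefficients or the interaction term let readers check that.
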